6.1.3 Treatments and Dosing

Eligible subjects in the DB phase will be randomized into 1 of 4 double-blind treatment arms using an interactive (voice/web) response system (IVRS/IWRS). The 4 treatment groups include (1) high-dose AZM (AZM-H), (2) intermediate-dose AZM (AZM-M), or (3) low-dose AZM (AZM-L) or (4) losartan.

The dose taken by each subject will be dependent on treatment assignment. All subjects randomized to AZM will initiate treatment at 10 mg. Subjects assigned to AZM-M will be force-titrated at Week 2 to the final randomized dose of 20 mg which will be maintained for the final 4 weeks of the DB Phase. Subjects assigned to the AZM-H group will be force-titrated at Week 2 to the final randomized dose of 40 mg or 80 mg, with the lower of the 2 possible doses being received by subjects who weigh <50 kg and the higher dose being received by subjects who are ≥ 50 kg. Similarly, subjects who are randomized to losartan will initiate treatment at a low dose (25/50 mg) and force titrated at Week 2 to the final losartan dose (50/100 mg). The low dose and final dose of losartan given is based on the subject's weight strata (25 to < 50 kg; ≥ 50 kg). Please see [Section 8.1.3](#) for more information on study medication.

In the Withdrawal Phase, subjects will be re-randomized using IVRS/IWRS to continue receiving their previously assigned active treatment or placebo.

At the beginning of the OL Phase, all subjects will be dispensed AZM 10 mg, which can be titrated to higher dose(s) (up to 40 mg for subjects <50 kg or up to 80 mg for subjects ≥ 50 kg) and additional medication(s) may be added if needed to achieve BP targets during the OL extension. Because body weight is likely to change, dose adjustments may occur during the OL Phase if growth assessments (height and weight) made at Week 8/Visit 9 or at any visit scheduled during the extension necessitate a dose by weight adjustment.

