If sponsor supplied drug (AZM, O/E losartan or placebo) is lost or damaged, the site can request a replacement from the IVRS/IWRS (refer to the system manual that will be provided separately). The MED ID numbers will be entered onto the eCRF.

Throughout all treatment phases, including the Placebo Run-in, study drug will be administered once daily, orally, with water, with or without food. Individual subjects or parents/legal guardians will be instructed to administer the medication at approximately the same time every day. In order to ensure that clinic BP measures are recorded at trough (ie, approximately 24 hours after the previous dose of study medication), clinic visits should be scheduled at approximately the same time as the medication is dosed. Subject will take their first dose of study medication in clinic.

The subjects or parents/legal guardians should be instructed by the investigator or designee that the AZM study medications are plain, white tablets in appearance. The desiccant is also white in appearance and that it should not be removed from the blister card and they are not to ingest the desiccants. The AZM tablets and O/E losartan capsules are to be swallowed whole. They are not to be chewed, crushed, or opened. Subjects or parents/legal guardians should also be instructed on the dosing procedures, dispensing instructions, and study medication storage requirements. They should also be instructed to withhold study medication on days that a clinic visit is scheduled. The study drug should be administered in the clinic after trough vital signs (BP and pulse rate) and other applicable procedures are recorded. All sponsor-supplied drug is to remain in original container until dose is to be dispensed.

Subjects or parents/legal guardians should be informed as follows if they miss a scheduled dose. If it is almost time for the next dose (within 12 hours), skip the missed dose and take the next dose when it is due. Otherwise, take the missed dose as soon as it is remembered, and then go back to taking the investigational drug as usual. Do not take a double dose to make up for a missed dose.

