For subjects who did not participate in the ABPM procedure, if the subject's seDBP remains <95 th percentile for age, gender, and height or <90 th percentile by age, gender, height if chronic renal disease, diabetes, heart failure or hypertensive target organ damage is present after the Washout/Placebo Run-in Phase (ie, does not satisfy inclusion criterion #4 on Day 1), the washout may be extended in 1-week increments up to 2 times (currently treated subjects only), for a maximum possible washout of 4 weeks, as long SBP also remains below this threshold. Placebo should be continued during the extension(s). Subjects whose seDBP remains below the entry criteria after the extensions will not be eligible for randomization to the DB Phase and shall be discontinued from the study and referred back to their treating physicians to resume appropriate antihypertensive treatment.

If the subject has satisfied all of the inclusion criteria and none of the exclusion criteria for randomization, the subject should be randomized using the IVRS/IWRS system, as described in [Section 8.3](#). The procedure for documenting run-in failures is provided in [Section 9.1.14](#).

9.3.4.2 Double-Blind Phase-Week 2/Visit 5

Visit can occur within a \pm 2 day window. The following procedures will be performed.

- Vital signs (including standing measurements).
- Concomitant medications.
- AE assessment.
- Urine pregnancy test performed at the site (female subjects \geq 12 years old and younger females deemed by the investigator to be of reproductive potential).
- Pregnancy avoidance counseling (female subjects \geq 12 years old and younger females deemed by the investigator to be of reproductive potential).
- Collection of double-blind study medication and compliance assessment. If required, counsel subject or parent/legal guardian on compliance.
- IVRS/IWRS access to dispense double-blind study medication and register study visit.
- Administration of the first dose of the newly assigned double-blind study medication in the clinic.
- Dispensing of new supply of double-blind study medication with dosing instructions.

9.3.4.3 Double-Blind Phase-Week 4/Visit 6

Visit can occur within a \pm 2 day window. The following procedures will be performed.

- Vital signs (including standing measurements).
- Concomitant medications.
- AE assessment.
- Clinical laboratory tests (renal subpanel).
- Pharmacokinetic sampling.

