3.3. TREATMENTS AND DOSING

Eligible subjects in the DB phase will be randomized into 1 of 4 DB treatment arms using an IVRS/IWRS. The 4 treatment groups include (1) AZM-L, (2) AZM-M, or (3) AZM-H or (4) losartan.

The dose (or tablet strengths) taken by each subject will be dependent on treatment assignment. All subjects randomized to AZM will initiate treatment at 10 mg. Subjects assigned to the AZM-M group will be forcetitrated at Week 2 to the final randomized dose of 20 mg which will be maintained for the final 4 weeks of the DB Phase. Subjects assigned to the AZM-H group will be force-titrated at Week 2 to the final randomized dose of 40 mg or 80 mg, with the lower of the 2 possible doses being received by subjects who weigh <50 kg and the higher dose being received by subjects who are ≥50 kg. Similarly, subjects who are randomized to losartan will initiate treatment at a low dose (25/50 mg) and force titrated at Week 2 to the final losartan dose (50/100 mg).

Similarly, subjects who are randomized to losartan and weighing < 50 kg will initiate treatment at the 25 mg dose and force titrated at Week 2 to the 50 mg losartan dose. Subjects who weigh $\ge 50 \text{ kg}$ will initiate treatment at 50 mg and forced titrated at Week 2 to the 100 mg losartan dose.

In the Withdrawal Phase, subjects will be re-randomized using IVRS/IWRS to continue receiving their previously assigned active treatment or placebo.

At the beginning of the OL Phase, all subjects will be dispensed AZM 10 mg, which can be titrated to higher dose(s) (up to 40 mg for subjects <50 kg or up to 80 mg for subjects ≥50 kg) and additional medication(s) may be added if needed to achieve BP targets during the OL extension. Because body weight is likely to change, dose adjustments may occur during the OL Phase if growth assessments (height and weight) made at Week 8/Visit 9 or at any visit scheduled during the extension necessitate a dose by weight adjustment. Refer to Table B: Treatment Arms for a summary of the 4 treatment arms.

Document: 2014-000674-18 Statistical Analysis Plan Version 7.0

Version Number:

Version Date:

7.0

13JAN2020

Template No.: CS_TP_BS016 Revision 5

Reference: CS_WI_BS005

Effective Date: 01Apr2018

Author:

and its subsidiaries. Unauthorized use, disclosure or reproduction is strictly prohibited.

7.0

Table B: Treatment Arms

Treatment	Body Weight	Double-Blind, Phase		Withdrawal Phase
	(a)	Wks 0-2	Wks 2-6	Wks 6-8

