15.4. EXPLORATORY EFFICACY

15.4.1. EXPLORATORY EFFICACY VARIABLES & DERIVATIONS

15.4.1.1.

Change from baseline to Week 6/Final Visit of the DB Phase and to Week 52/Final Visit of the OL Phase in 24hour, 12-hour, daytime, night time, and trough DBP and SBP by ABPM.

15.4.1.2.

AZM dose response for change from Baseline to Week 6/Final Visit of the DB Phase, Week 2 and Week 4 of the DB Phase in clinic seDBP, seSBP and MAP.

15.4.1.3.

Primary endpoint and secondary endpoints for subgroup analysis.

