15.4.3. Analysis of Exploratory Efficacy Variables

15.4.3.1.

For Change from Baseline to Week 6/Final Visit of the DB Phase in 24-hour, 12-hour, daytime, night time, and trough DBP and SBP by ABPM, descriptive statistics will be provided for the change from Baseline as well as the difference between each AZM treatment and losartan for 24-hour, 12-hour, daytime, night time, and trough ABPM SBP/DBP. For Change from Baseline to Week 52/Final Visit of the OL Phase in 24-hour, 12hour, daytime, night time, and trough DBP and SBP by ABPM, descriptive statistics will be provided for the change from Baseline for 24-hour, 12-hour, daytime, night time, and trough ABPM SBP/DBP.

2014-000674-18 Statistical Analysis Plan Version 7.0 Version Number: 7.0 Document: Author: Version Date: 13JAN2020

Template No.: CS_TP_BS016 Revision 5 Reference: CS_WI_BS005

Effective Date: 01Apr2018

Daytime is defined as 6 am – 9:59 pm Nighttime is defined as 10 pm - 5:59 am

Profile plots (line with symbol at each visit with +/- 1 SE error bars) will be displayed for the observed seDBP and seSBP and the change in seDBP and seSBP from baseline to Week 6 and to Week 52 in 24-hour, 12-hour, daytime, night time by ABPM.

15.4.3.2.

Exploratory dose response analysis using only AZM low, med and high dose groups, for change from Baseline to Week 6/ Final Visit, Week 2, Week 4 of the DB Phase in clinic seDBP, seSBP and MAP will be performed using linear regression model with weight adjusted dose (mg/kg) as the continuous covariate. LOCF will be used for missing data. The intercept with Standard Error and estimate of the coefficient with Standard Error will be displayed with the summaries. Additionally, an ANCOVA with treatment, age and weight as fixed effects, and baseline seDBP, seSBP or MAP as covariate will be performed to assess between-group comparisons.

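### The exploratory mg/kg regression cannot show dose response at Week 2, when every AZM arm has taken only 10 mg; at Weeks 4 and 6 it omits baseline BP and is partly confounded with body weight

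*SAP*

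**What the plan says.** SAP 15.4.1.2 lists the variable as "AZM dose response for change from Baseline to Week 6/Final Visit of the DB Phase, Week 2 and Week 4 of the DB Phase". SAP 15.4.3.2 describes an "Exploratory dose response analysis using only AZM low, med and high dose groups", to be run for "Week 6/ Final Visit, Week 2, Week 4 of the DB Phase in clinic seDBP, seSBP and MAP", "using linear regression model with weight adjusted dose (mg/kg) as the continuous covariate". It displays an intercept and one coefficient, each with a standard error. SAP 15.4.2.2 fills missing values by LOCF. The same paragraph of 15.4.3.2 adds a separate ANCOVA between arms, with age, weight and baseline BP terms.

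On dosing, Protocol 6.1.3 states: "All subjects randomized to AZM will initiate treatment at 10 mg". SAP 3.3 states: "Subjects assigned to the AZM-H group will be force-titrated at Week 2 to the final randomized dose of 40 mg or 80 mg". AZM-M moves to 20 mg at the same visit and AZM-L stays at 10 mg (Protocol Figure 8.a, SAP Table B). On the order of events at a visit, Protocol 8.2 states: "The study drug should be administered in the clinic after trough vital signs (BP and pulse rate) and other applicable procedures are recorded". The Week 2 procedures in Protocol 9.3.4.2 begin with vital signs and later list "Administration of the first dose of the newly assigned double-blind study medication in the clinic".

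Protocol 5.2.5 and SAP 6.3 name the dose-response endpoint at Week 6/Final Visit only. Protocol 13.1.3 commits to the regression for Week 6 seDBP and makes other parameters and DB visits optional. SAP 15.4.3.2 makes them planned analyses.

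**The concern.** A dose-response slope is informative when the dose differs between subjects by randomisation. At Week 2 it does not yet differ, so a table headed as dose response would show something else: how the response to one common dose varies with body size.

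At Weeks 4 and 6 the single regressor combines randomised dose with body weight. If BP change is related to weight for other reasons, part of that relation enters the slope. The model also leaves out baseline BP, although the SAP's other BP-change models carry a baseline or Week 6 value. At stake is the reading of a secondary description of dose, not a confirmatory claim.

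**Working it through.** The documents give no power, precision or sample-size figure for this regression, so there is none to reproduce.

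**Step 1. Dose taken before each BP reading.** Titrated supply is first dispensed and taken at the Week 2 visit, after the trough reading. The Week 2 BP therefore reflects 10 mg in all three arms. Week 4 and Week 6 readings follow the final doses.

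**Step 2. mg/kg = dose / weight.**

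| Weight | Week 2, dose taken, all arms | Weeks 4 and 6: L | M | H |
|---|---|---|---|---|
| 25 kg | 10/25 = 0.40 | 0.40 | 20/25 = 0.80 | 40/25 = 1.60 |
| 50 kg | 10/50 = 0.20 | 0.20 | 20/50 = 0.40 | 80/50 = 1.60 |
| 75 kg | 10/75 = 0.133 | 0.133 | 20/75 = 0.267 | 80/75 = 1.067 |
| 100 kg | 10/100 = 0.10 | 0.10 | 20/100 = 0.20 | 80/100 = 0.80 |

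At Week 2 all variation in mg/kg is variation in 1/weight. The SAP does not say whether dose taken or assigned dose is meant. If assigned dose is used, the regressor is the Weeks 4 and 6 block of the table, which no subject has yet received.

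**Step 3. Simulation of the regression as written.**
- From the documents: 52 subjects per arm and SD 8.3 (Protocol 13.3; that SD is for the Week 6 to Week 8 change and stands in here for change from baseline), 80% of subjects at 50 kg or more (the cap in Protocol 6.2.2), minimum weight 25 kg (Protocol 7.1).
- Assumed: weights uniform on 25–50 and 50–110 kg; baseline SD 7 mm Hg with slope −0.4 on change, so the baseline–change correlation is 0.4 × 7 / 8.3 = 0.34 in size; a smaller BP fall in heavier subjects of 0, 0.5 or 1.0 mm Hg per 10 kg.
- 3,000 runs per scenario, so a 5% rate carries a simulation error of √(0.05 × 0.95 / 3000) = 0.4 percentage points.

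Results with no true dose effect, as the proportion of trials with slope p<0.05:

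| Weight trend, mm Hg per 10 kg | 0 | 0.5 | 1.0 |
|---|---|---|---|
| Week 2, as written, dose taken | 5.2% | 35.6% | 88.4% |
| Week 6, as written | 5.3% | 7.2% | 15.5% |
| Week 6, plus baseline BP and weight | 5.7% | 4.6% | 4.9% |
| Week 6 mean slope as written, mm Hg per mg/kg | 0.0 | −0.8 | −1.5 |

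With assigned dose at Week 2 and a trend of 1.0, the rate is 16.2%. At Week 6, 1/weight explains 7.8% of the variance of mg/kg. With 60% of subjects at 50 kg or more, that share is 10% and the Week 6 rate at a trend of 1.0 is 19.0% (2,000 runs). With a true slope of −5 and a trend of 1.0, the mean slope is −6.5 as written and −5.0 adjusted. Doses at Week 4 are the same as at Week 6, so these results apply there under the same assumptions.

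**Step 4. Can adjustment rescue Week 2?** No. The correlation of 10/weight with weight is −0.93. Adding weight and baseline raises the slope's standard error from 9.7 to 24.4, and no randomised contrast is recovered.

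**Step 5. Precision at Week 6, no trend.** The slope's standard error is 1.563 as written, 1.476 with baseline added (1.476/1.563 = 0.944, about 6% lower), and 1.543 with baseline and weight. The weight term alone costs 1.543/1.476 = 1.045, about 4.5%. In general the baseline term multiplies the standard error by √(1 − r²): 0.98 at r = 0.2, 0.92 at r = 0.4, 0.80 at r = 0.6.

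**The case against.** The strongest reply is that little depends on this slope. The named endpoint is Week 6 only, the regression is outside the sequence in SAP 7.4, and 15.4.3.2 attaches no p-value or decision rule to it. That stands. The rejection rates above measure susceptibility to bias; they are not error rates of a planned test. A reader might take the 36% to 88% at Week 2 as the false-positive rate of the dose-response endpoint. The documents do not support that.

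Second, mg/kg is meant to place 10 mg at 25 kg and 20 mg at 50 kg at the same point, since doses were chosen by weight band to match exposure (Protocol 6.2.2). This also stands. Week 2 mg/kg is non-randomised exposure information, so it would be wrong to say that it carries no information at all.

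Third, dose can be read in other ways. The MMRM in SAP 15.2.3.2 gives arm estimates adjusted for baseline, weight, Tanner stage and race, and Protocol 13.1.4 allows a concentration–response model. This regression is therefore not the only route to dose response. None of these analyses corrects the slope, however, and at Week 2 the arm comparison also sets identical doses against each other.

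Fourth, the trends are assumed and not small. Across 25–110 kg they amount to 85 × 0.05 = 4.25 and 85 × 0.10 = 8.5 mm Hg, against a design difference of 4.5 mm Hg. With no trend, the Week 6 regression behaves correctly as written.

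**Conclusion.** The Week 2 finding is firm and needs nothing beyond the dosing table and the order of procedures: the slope contains no randomised dose contrast under either definition of dose, and cannot be read as dose response.

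At Weeks 4 and 6 the problem is partial. A reader might infer that the Week 6 slope is essentially a weight effect. It is not: about 92% of the variance of mg/kg is not explained by 1/weight under the assumed weights, and the excess over 5% ranges from nothing to about 10 percentage points across the assumed trends. A reader might also expect adjustment for baseline and weight to raise power markedly. That depends on a baseline correlation the documents do not give. With a true slope of −5, no weight trend and a correlation of 0.34, power is 89.7% as written and 90.1% with both terms. Leaving out baseline BP is a modest, avoidable loss of precision. The primary conclusion is unaffected.

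**What to change.** - Remove Week 2 from SAP 15.4.1.2 and 15.4.3.2, or retitle that output as response to 10 mg by body weight. The protocol's optional wording for other visits permits either.
- At Weeks 4 and 6, add the baseline value of the parameter analysed to the regression.
- Report the Week 4 and 6 slope also adjusted for body weight and the stratification factors (Tanner stage and race) as a sensitivity analysis. The weight term guards against confounding but can cost some precision if response truly follows mg/kg, so it should sit beside the main slope and not replace it.
- State which dose and which weight define mg/kg, including for LOCF values, since a Week 2 reading taken on 10 mg can be carried into Weeks 4 and 6.

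The cost is a few SAP sentences, one model term and one sensitivity output per parameter and visit, all from data already collected. The Week 2 outputs are lost or retitled. The change should precede the unblinding described in SAP 4.2; if made later, it should be labelled post hoc.

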4.1.4.1 Short-Term Placebo and/or Active-Controlled Monotherapy Studies

Statistically significant reductions in SBP and diastolic blood pressure (DBP) were observed with AZM compared with placebo and comparators (olmesartan medoxomil 40 mg and valsartan 320 mg). During treatment with AZM, most of the blood pressure (BP) reduction was observed at Week 2 and reached plateau by Week 4. Changes in clinic and ambulatory BP were consistent. There was a clinically meaningful yet diminished treatment response in Black subjects relative to White subjects or subjects of other race.

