3.2. RANDOMIZATION

The investigator or investigator's designee will access the interactive (voice/web) response system (IVRS/IWRS) at Screening to obtain the subject's study number. The investigator or the investigator's designee will utilize the IVRS/IWRS to enter the subject into the Placebo Run-in Phase. The IVRS/IWRS will also be used to randomize the subject into the DB Phase and later the Withdrawal Phase. The DB Phase

Document: 2014-000674-18 Statistical Analysis Plan Version 7.0 Version Number: 7.0

Author: Version Date: 13JAN2020

Template No.: CS_TP_BS016 Revision 5 Reference: CS_WI_BS005

Effective Date: 01Apr2018

randomization will be stratified by age (Tanner stage <3, ≥3), weight (≥25 to <50 kg, ≥50 kg), and race (non-Black, Black).

Enrolment caps will also be applied to randomization to ensure a percentage of subjects with secondary hypertension of approximately 40%-60% and to ensure that no more than \approx 25% of subjects are post-renal transplant subjects and no more than \approx 60% of subjects weigh greater than or equal to 50 kg at Baseline. Randomization for the Withdrawal Phase will be stratified by the treatment received in the DB Phase (i.e., AZM-L, AZM-M, or AZM-H or losartan).

Protocol Amendment 01, dated 12 Dec 2018, revised the number of secondary hypertensive subjects and < 50 kg subjects due to difficulty in recruiting these subpopulations. The expected number of secondary hypertensive subjects and subjects weighing less than 50 kg was not achieved. The revised expected percentage of subjects with secondary hypertension and subjects weighing less than 50 kg will be at least 20% of the total subject population.

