15.1.3. Primary Analysis of Primary Efficacy Variable(s)

The primary objective of this study is to evaluate the antihypertensive effect of AZM compared with placebo after a randomized, double-blind, withdrawal (Withdrawal Phase).

The primary efficacy analysis will be performed for the FAS. The primary analysis will exclude subjects that were treated with losartan during the DB Phase.

The primary efficacy variable analysis will be an ANCOVA model with treatment (AZM low, med, high and placebo), age (Tanner stage <3, ≥3), race (Black or African American, Non- Black or African American) and weight (<50 kg, ≥50 kg) as fixed effects, and Week 6/Final Visit of the DB Phase seDBP as a covariate. The primary comparison, mean (i.e. pooled) AZM effect versus placebo, will be made using an ANCOVA contrast statement. Comparisons between each AZM dose to placebo will also be done from the framework of the above ANCOVA using contrast statements.

To control for multiplicity of the type 1 error, the sequential testing procedure mentioned in Section 7.4 will be employed in the analysis of the primary endpoint.

Summary of observed seDBP at Week 6 and Week 8 will be presented. Change in seDBP from Week 6 to Week 8 and the results from the analysis (Least square (LS) means, Standard Error, LS Mean Difference (SE), P-value and 95% Confidence Interval for Difference in LS means) will also be presented.

Profile plots (line with symbol at each visit with +/- 1 SE error bars) will be displayed for observed seDBP and boxplot will be displayed for the change in seDBP from Week 6 to Week 8.

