15.2.3. Analysis of Secondary Efficacy Variables

15.2.3.1.

Change from Week 6/Final Visit of the DB Phase to Week 8/Final Visit of the Withdrawal Phase in trough clinic seSBP and MAP will be analyzed using an ANCOVA model with treatment (AZM low, med, high and placebo), age (Tanner stage <3, ≥3), race (Black or African American, Non- Black or African American) and weight (<50 kg, ≥50 kg) as fixed effects, and baseline value (seDBP or MAP) as a covariate. The comparison, mean (i.e., pooled) AZM effect versus placebo, will be made using an ANCOVA contrast statement. Comparisons between each AZM dose to placebo will also be done from the framework of the above ANCOVA using contrast statements.

This analysis will exclude subjects that were treated with losartan during the DB Phase. There will be no sequential testing procedure for this analysis.

Profile plots (line with symbol at each visit with +/- 1 SE error bars) will be displayed for observed seSBP and MAP and boxplot will be displayed for the change in seSBP and MAP from Week 6 to Week 8.

15.2.3.2.

Change from baseline in trough clinic seDBP, seSBP, and MAP at Week 6/Final Visit, will be analyzed with a mixed models for repeated measure (MMRM) with treatment (AZM low, med, high dose and losartan), time point (Week 2, Week 4, Week 6), treatment by time interaction, age (Tanner stage <3, ≥3), race (Black or African American, Non- Black or African American) and weight (<50 kg, ≥50 kg) as fixed effects, and corresponding baseline value (seDBP, seSBP, MAP) as a covariate. An unstructured covariance matrix will be used to model the within-subject variation-covariance errors. The comparison, mean (i.e., pooled) AZM effect versus losartan, will be made using contrast statement. Comparisons between each AZM dose to losartan will be done from the framework of the above MMRM. Observed data will be used to perform MMRM. Sensitivity analyses will be performed including ANCOVA at each time point using last observation carried forward (LOCF).

In case of non-convergence, the following tests in sequence will be used: heterogeneous Toeplitz covariance structure, heterogeneous autoregressive covariance structure, heterogeneous compound symmetry covariance structure.

Profile plots (line with symbol at each visit with +/- 1 SE error bars) will be displayed for the change in seDBP, seSBP and seMAP from baseline to Week 6.

15.2.3.3.

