The analysis of subject who achieves target BP (seDBP, seSBP, both) at Week 8/Final Visit of the Withdrawal Phase, with the target defined as <90th percentile for age, gender, and height, will be conducted using logistic models with treatment (AZM low, med, high and placebo), age (Tanner stage <3, ≥3), race (Black or African American, Non- Black or African American)and weight (<50 kg, ≥50 kg) as fixed effects and baseline clinic seated BP as a covariate. The analysis will be based on LOCF data. Sensitivity analysis will be done using multiple imputation. The number and percentage of subjects who achieved target BP at Week 8/Final Visit of the Withdrawal Phase will be presented, along with the odds ratios and associated 95% CIs. Percentage will be calculated as:

Number of subjects with target blood pressure / Number of subjects with BP at week 8Profile plots (line with

Document: 2014-000674-18 Statistical Analysis Plan Version 7.0 Version Number: 7.0

Author: Version Date: 13JAN2020

Template No.: CS_TP_BS016 Revision 5 Reference: CS_WI_BS005

Effective Date: 01Apr2018

symbol at each visit with +/- 1 SE error bars) will be displayed for the change in seDBP, seSBP and seMAP from baseline to Week 8.

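### The exploratory between-dose ANCOVA omits race, a randomisation stratum, so its reported standard errors may be slightly too wide (by 0% to about 3.6%)

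*SAP*

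**What the plan says.** The Double-Blind (DB) Phase has three stratification factors. SAP 3.2 states that "randomization will be stratified by age (Tanner stage <3, ≥3), weight (≥25 to <50 kg, ≥50 kg), and race (non-Black, Black"), and Protocol 6.1.6 and 8.3 agree.

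SAP 7.1 lists race group among the model factors but leaves its use to each analysis section. Those sections read as follows:

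- **Primary ANCOVA (SAP 15.1.3):** includes "race (Black or African American, Non- Black or African American) and weight (<50 kg, ≥50 kg) as fixed effects, and Week 6/Final Visit" seDBP. The observed-data sensitivity analysis (15.1.4) uses the same model, and the Appendix 5 code carries the race variable.
- **seSBP and MAP ANCOVA, Week 6 to Week 8 (15.2.3.1):** race included.
- **DB Phase MMRM (15.2.3.2):** includes "treatment by time interaction, age (Tanner stage <3, ≥3), race", and is reused for Weeks 2 and 4 (15.3.3.1).
- **Target-BP analyses:** the Week 8 analysis (15.2.3.3) "will be conducted using logistic models with treatment", Tanner stage, race and weight. The Week 6 and CKD logistic models (15.3.3.3) also include race.
- **Between-dose ANCOVA (15.4.3.2):** "an ANCOVA with treatment, age and weight as fixed effects, and baseline seDBP, seSBP or MAP as covariate". Race is not named.

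Two other places show no race term. The mg/kg dose regression in the same paragraph of 15.4.3.2 names no covariate other than dose. The LOCF sensitivity ANCOVA in 15.2.3.2 does not list its terms.

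Protocol 13.1.3 describes the same between-dose ANCOVA, also without race. None of the protocol's efficacy models includes race.

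**The concern.** An analysis should normally adjust for the factors used to stratify the randomisation. The SAP does so almost everywhere, adding race to models that lacked it in the protocol. The sentence in 15.4.3.2 still follows the protocol's wording and gives no reason for differing. SAP 3.6, on changes from the protocol, points only to the sample-size section. This looks like an oversight.

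There is some reason to expect race to matter. Of adults treated with AZM, Protocol 4.1.4.1 says: "There was a clinically meaningful yet diminished treatment response in Black subjects relative to White subjects or subjects of other race". The analysis here is described as an "Exploratory dose response analysis using only AZM low, med and high dose groups", so every child in it takes AZM. A race difference in response would therefore appear largely as a race main effect on change from baseline, which is the variance a race term removes.

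At stake is the width of the reported intervals for the dose differences at Weeks 2, 4 and 6.

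**Working it through.** **The plan's own figures.** The documents give no SD, power or sample-size figure for the between-dose ANCOVA. The only planning figures are for the primary comparison (Protocol 13.3), and they reproduce for a two-sided 5% two-sample t-test of 4.5 mm Hg:

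- Original: 195 × 0.9 = 175.5 AZM subjects, split 1:1, SD 10.5. Power is 80.6%, against 80% stated.
- Revised: 3 × 52 × 0.9 = 140.4 AZM subjects, split 1:1, SD 8.3. Power is 89.1%, consistent with the stated figure of more than 80%.

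**Inputs for the check**

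- Residual SD with race in the model: s = 8.3 mm Hg. Protocol 13.3 gives this for the Week 6 to Week 8 change. No SD is given for change from Baseline, so it is a stand-in.
- Subjects per arm: 52 (Protocol 13.3).
- Share of Black subjects: q = 10% to 30%. Assumed; not in the documents.
- Race difference in BP change: d = 0 to 5 mm Hg. Assumed; Protocol 4.1.4.1 is qualitative and concerns adults.

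**Formulas.** With race balanced across arms, omitting it adds q(1 − q)d² to the residual variance. The reported SE of a dose difference is s√(2/52) with race in the model, and it is multiplied by R = √(1 + q(1 − q)d²/s²) without race. Adding race lowers it by 1 − 1/R. Here s² = 68.89 and 8.3 × √(2/52) = 1.628 mm Hg.

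| q | d (mm Hg) | q(1 − q)d² | R | SE without race | Reduction from adding race |
|---|---|---|---|---|---|
| 10% or 30% | 0 | 0 | 1.000 | 1.628 | 0% |
| 10% | 2 | 0.36 | 1.003 | 1.632 | 0.3% |
| 10% | 5 | 2.25 | 1.016 | 1.654 | 1.6% |
| 30% | 2 | 0.84 | 1.006 | 1.638 | 0.6% |
| 30% | 3 | 1.89 | 1.014 | 1.650 | 1.3% |
| 30% | 5 | 5.25 | 1.037 | 1.689 | 3.6% |

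In the last row the 95% half-width is 1.96 × 1.689 = 3.31 mm Hg, against 1.96 × 1.628 = 3.19 mm Hg with race. The critical value becomes 1.96 × 1.037 = 2.03 true standard errors, so a nominal 5% test has a level of about 4.2%.

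**Does the estimate itself become less precise?** Three arms of 52 were simulated with randomisation stratified by race, 4,000 runs per scenario. Results for q = 30%:

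| d (mm Hg) | Actual SD of estimate, without / with race | Mean reported SE, without / with race | Rejection rate under the null, without / with race |
|---|---|---|---|
| 0 | 1.632 / 1.633 | 1.630 / 1.631 | 5.1% / 5.1% |
| 3 | 1.604 / 1.604 | 1.653 / 1.631 | 4.0% / 4.3% |
| 5 | 1.665 / 1.665 | 1.694 / 1.632 | 4.7% / 5.5% |

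The Monte Carlo error of a 5% rate is √(0.05 × 0.95/4000) = 0.34 percentage points. The actual spread is the same with or without race. Only the reported SE differs, and rejection is slightly less frequent when a prognostic race factor is omitted.

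**The case against.** The case against has real force. The analysis is exploratory, comes second to the mg/kg regression, and lies outside the sequential testing procedure of SAP 7.4. No decision or power statement in the documents rests on it. The SAP follows Protocol 13.1.3 here, so there is no conflict between the two documents. The choice of covariates for such a model is partly a matter of preference. The race mix and the race effect are unknown, and the gain may be nil. All of this stands, and it limits the point to a minor one. It does not explain why this model alone, among the between-group efficacy models with listed terms, omits a stratum.

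A reader might infer three stronger things that the documents do not support:

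- **That the dose comparisons lose true precision or are invalid.** Stratification already balances race, so the estimate's spread is essentially unchanged. The error is in the reported SE, and it is on the conservative side.
- **That adding race would align the Week 6 dose contrasts with the MMRM.** It would not. The MMRM is a repeated-measures model of observed data that includes losartan (15.2.3.2). This ANCOVA uses only the AZM arms, with LOCF specified for the dose-response analysis (15.4.2.2).
- **That every other efficacy model in the SAP adjusts for race.** The mg/kg regression does not, and the LOCF sensitivity ANCOVA does not say.

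**Conclusion.** The point holds as a minor consistency and efficiency improvement. There is no bias and no type I inflation. If race predicts change in blood pressure in these children, the reported intervals for the dose differences are slightly too wide; if it does not, nothing is lost.

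The size rests on the assumed race share and race difference, on the borrowed SD, and on race being balanced across arms and unrelated to the other model terms. Overlap between race and Tanner stage, weight or baseline pressure would shrink the gain. The omission is certain from the text; the size of the benefit is not.

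**What to change.** Reword the ANCOVA sentence in SAP 15.4.3.2 along these lines:

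> Between-dose ANCOVA. Fixed effects: treatment, age (Tanner stage <3, ≥3), race (Black or African American, Non-Black or African American) and weight (<50 kg, ≥50 kg). Covariate: the corresponding baseline value of seDBP, seSBP or MAP.

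If race was left out on purpose, one sentence giving the reason would do instead. It would also help to state the terms of the LOCF sensitivity ANCOVA in 15.2.3.2.

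The cost is one model term and one degree of freedom. Race is already collected and coded for the other models, and no procedure or data collection changes. The edit should be settled before treatment assignments are unblinded for the DB and Withdrawal Phase analysis (SAP 4.2).
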